**NCT02358993**

**April 4, 2019**

# Protocol Details

## Basic Info

Confirmation Number: **cihdibib**  
Protocol Number: **820117**  
Created By: **[name]**  
Principal Investigator: **[name]**  
Protocol Title: **The Efficacy and Cost-Effectiveness of a 24-hour course of Methenamine Hippurate For Preventing Post-Operative Urinary Tract Infection**  
Short Title: **Short-Course Methamine Hippurate for Prevention of Post-Operative UTI**  
Protocol Description: **We will determine the efficacy of an innovative short regimen of methenamine hippurate on prevention of post-operative UTI in patients requiring short-term catheterization after pelvic reconstructive surgery through a randomized, double-blinded, placebo-controlled trial. Primary outcome will be the rate of symptomatic UTI within 3 weeks of surgery. We will study cost-effectiveness, antibiotic resistance profiles, and adverse drug effects. Findings may reduce antibiotic use and nosocomial UTIs.**  
Submission Type: **Biomedical Research**  
Application Type: **FULL**

## Resubmission\*

Yes

## Hospital Sites

Will any research activities and/or services be conducted at a Penn Medicine affiliated hospital site?

No

**Responsible Org (Department/School/Division):**

4333 - OB-Obstetrics and Gynecology

#### **Disclosure of Significant Financial Interests\***

Does any person who is responsible for the design, conduct, or reporting of this research protocol have a **FINANCIAL INTEREST?**

No

#### **Penn Intellectual Property\***

To the best of the Principal Investigator's knowledge, does this protocol involve the testing, development or evaluation of a drug, device, product, or other type of intellectual property (IP) that is owned by or assigned to the University of Pennsylvania?

#### **Certification**

I have reviewed the *Financial Disclosure and Presumptively Prohibited Conflicts for Faculty Participating in Clinical Trials* and the *Financial Disclosure Policy for Research and Sponsored Projects* with all persons who are responsible for the design, conduct, or reporting of this research; and all required Disclosures have been attached to this application.

Yes

## **Biomedical Research**

#### **Clinical Trial\***

Is this a clinical trial?

#### **Investigator Initiated Trial\***

Is this an investigator initiated trial?

Yes

If Yes, please be aware that the investigator may be required to create and manage a record of this trial in <https://clinicaltrials.gov>.

#### **Drugs or Devices\***

Does this research study involve Drugs or Devices?

Yes: Drugs, products or devices are used in accordance with FDA approval.

#### **IND Exemption**

**For studies that fall under an IND exemption, please provide the number below**

**For studies including IND or IDE's, please provide the number(s) below**

#### **IDE Review\***

NOTE: For research involving investigational devices, you are required to review the guidance on Managing Research Device Inventory. Consult the Penn Manual for Clinical Research: <https://www.med.upenn.edu/pennmanual/secure/investigational-product-management-at-sites-not-using-investigational-drug-services-ids.html> Please check the box Yes if you have reviewed the guidance.

Yes

**Research Device Management\***

Please indicate how research device(s) will be managed.

Not Applicable (no investigational devices)

**Drug, Herbal Product or Other Chemical Element Management \***

Please indicate how drugs, herbal products or other chemical entities will be managed.

The drug, herbal product or other chemical entity will be received, stored and dispensed by the research team (please provide information in the protocol summary as to how this will be conducted)

**Radiation Exposure\***

Are research subjects receiving any radiation exposure (e.g. X-rays, CT, Fluoroscopy, DEXA, pQCT, FDG, Tc-99m, etc.) that they would not receive if they were not enrolled in this protocol?

No

**Gene Transfer\***

Does this research involve gene transfer (including all vectors) to human subjects?

No

**Human Source Material\***

Does this research include collection or use of human source material (i.e., human blood, blood products, tissues or body fluids)?

Yes

**CACTIS and CT Studies\***

Does the research involve Center for Advanced Computed Tomography Imaging Services (CACTIS) and CT studies that research subjects would not receive if they were not part of this protocol?

No

**CAMRIS and MRI Studies\***

Does the research involve Center for Advanced Magnetic Resonance Imaging and Spectroscopy (CAMRIS) and MRI studies that research subjects would not receive if they were not part of this protocol?

No

**Investigational Agent or Device within the Operating Room\***

Does the research project involve the use of an investigational agent or device within the Operating Room?

No

**Cancer Related research not being conducted by an NCI cooperative group\***

Does this protocol involve cancer-related studies in any of the following categories?

No

**Processing of Materials\***

Will the research involve processing (such as over encapsulating, or compounding)?

Yes

**In-House Manufacturing of Materials\***

Will the research involve processing (such as over encapsulating, or compounding)?

Yes

**Medical Information Disclosure\***

Does the research proposal involve the use and disclosure of research subject's medical information for research purposes?

Yes

**If the answer is YES, indicate which items is is provided with this submission:**

Modified research informed consent document that incorporates HIPAA requirements

**CTRC Resources\***

Does the research involve CTRC resources?

No

**Pathology and Laboratory Medicine Resources\***

Will samples be collected by hospital phlebotomy and/or processed or analyzed by any of the clinical laboratories of the University of Pennsylvania Health System?

Yes

**Clinical Laboratory Services\***

Will samples be collected by UPHS phlebotomy and/or analyzed by the hospital laboratory?

No

**Anatomic Pathology Services\***

Will tissue specimens (other than blood) be collected for clinical, diagnostic, or research purposes OR be processed through surgical pathology, cytopathology, neuropathology, or hematopathology?

No

**Research Involves Apheresis, Cell Collection, and/or Blood Product Collection\***

Does this research involve collection of blood products in the Penn Donor Center and/or the use of apheresis for treatment or collection of cells or other blood components?

No

**Research involving blood transfusion or drug infusions\***

Will your research involve blood transfusion or infusion of study drug in 3 Ravdin Apheresis Unit for research purposes?

No

**Trial in Radiation Oncology**

Is this research a prospective trial being done in Radiation Oncology, and if so, has this protocol been approved by the Radiation Oncology Protocol committee?

N/A

**Study in Radiation Oncology**

Is this research a retrospective study being done in Radiation Oncology, and if so, has this project been reviewed by the Radiation Oncology Clinical Research Group?

N/A

**Use of UPHS services\***

Does your study require the use of University of Pennsylvania Health System (UPHS) services, tests or procedures\*, whether considered routine care or strictly for research purposes?

Yes

**Primary Focus\***

Clinical Trial (prospectively assigning subjects to health-related interventions to evaluate outcomes)

**Protocol Interventions**

**Sociobehavioral (i.e. cognitive or behavioral therapy)**

**Drug**

**Device - therapeutic**

**Device - diagnostic (assessing a device for sensitivity or specificity in disease diagnosis)**

**Surgical**

**Diagnostic test/procedure (research-related diagnostic test or procedure)**

**Obtaining human tissue for basic research or biospecimen bank**

**Survey instrument**

**None of the above**

**The following documents are currently attached to this item:**

*There are no documents attached for this item.*

**Department budget code**

None

## **Multi-Center Research**

**Penn as lead**

1. Is this a multi-center study where Penn is serving as the Lead Site or the Penn PI is serving as the Lead Investigator?

**Management of Information for Multi-Center Research**

Not Applicable

**Penn irb of record**

2. Is this a multi-center study where the Penn IRB will be asked to serve as the IRB of Record for other external study sites?

**Other Sites**

No other sites

## **Protocol**

**Abstract**

Catheter-associated urinary tract infection (UTI) is the most common post-operative nosocomial infection. An agent that prevents catheter-associated UTI but is not associated with antibiotic resistance is not known. Methenamine hippurate has similar pharmacokinetics as short-course antibiotics that prevent catheter-associated UTI, such as ciprofloxacin. Our aim is to compare the efficacy of an innovative short regimen of methenamine hippurate, an antiseptic that is converted into formaldehyde in urine, with the efficacy of short-course ciprofloxacin for preventing post-operative UTI in urogynecologic surgery. We propose a randomized, blinded non-inferiority trial to determine the efficacy of two doses of methenamine hippurate compared with the urology standard of fluoroquinolones at catheter withdrawal for reducing post-operative UTI in patients requiring short-term indwelling catheterization after pelvic reconstructive surgery. The primary outcome will be the rate of symptomatic UTI requiring treatment within three weeks of surgery. We will perform cost-effectiveness analysis comparing the cost of prophylaxis with methenamine to the cost of prophylaxis with ciprofloxacin. We plan to describe the resistance profile of positive urine cultures and adverse effects of methenamine. This study is innovative because it involves 1) a two-dose regimen of a non-antibiotic prophylactic and 2) cost-effectiveness analysis. The findings will help reduce the rate of antibiotic use and nosocomial UTIs, which are associated with morbidity and serve as important indicators of quality of care.

**Objectives**

**Overall objectives**

SPECIFIC AIMS Primary Aim: To determine if the efficacy of prophylaxis with a 24 hour course of methenamine hippurate (two doses) is non-inferior to the efficacy of a 24-hour course of fluoroquinolones in prevention of post-operative urinary tract infections after short-term indwelling catheterization following surgery for pelvic floor disorders. Secondary aim: - To determine if prophylaxis with methenamine hippurate is more cost-effective than prophylaxis with fluoroquinolones

in patients undergoing short-term indwelling catheterization. - To determine the antibiotic resistance profile of post-operative urinary tract infections that develop after short-term indwelling catheterization after surgery for pelvic floor disorders, with methenamine as compared to fluoroquinolones. - To determine the prevalence of side effects that may accompany use of methenamine hippurate prophylaxis. - To describe factors that influence patient medication compliance with short-term methenamine hippurate and ciprofloxacin prophylaxis.

#### **Primary outcome variable(s)**

PRIMARY OUTCOME: Treatment of clinically suspected UTI within three weeks of surgery. This is defined as any symptomatic UTI requiring treatment with antibiotics as determined by the development of 2 or more of the following symptoms, in the absence of vaginal symptoms: urinary frequency; urinary urgency; dysuria; fever over 38°C/100.4°F; suprapubic, flank, or back pain; and/or chills. Patients will be encouraged to undergo urine culture prior to empiric treatment, but a positive urine culture will not be required as part of the primary outcome. We feel that this more accurately reflects the diagnosis and treatment of UTI in the clinical setting as: 1) it may not always be possible to delay treatment until patients are able to undergo urine culture; 2) accuracy of self-reported symptoms for the diagnosis of UTI is high; 3) the probability of UTI in patients with combinations of symptoms is very high.

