#### **Key inclusion criteria**

Inclusion criteria: female; patients who are able to read and write English; 18 years of age or older; underwent surgery for pelvic organ prolapse, urinary incontinence, or both; require post-operative short-term transurethral catheterization for greater than 24 hours.

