**Procedures**

**RECRUITMENT** We plan to recruit women from 3 clinical sites associated with 3 departments in the University of Pennsylvania Health System: 1) Urogynecology at Hospital of University of Pennsylvania (HUP), 2) Urogynecology at Pennsylvania Hospital (PAH) and 3) Urology at Pennsylvania Hospital (PAH). Physician investigators, who are present at all sites, will screen patients planning for surgery for pelvic organ prolapse, urinary incontinence, or both, for participation. Following confirmation of eligibility, the physicians will obtain informed consent prior to surgery at the planned preoperative visit. Last year, the combined surgical volume of these cases at our three clinics was 532 subjects; thus, we anticipate we will be able to easily recruit the proposed sample size in twelve months. **ENROLLMENT AND BASELINE VISIT:** Patients who are being discharged home with an indwelling catheter following pelvic reconstructive surgery will be enrolled into the study. With regards to outpatient surgery (such as a suburethral sling), this will occur within a few hours after surgery for patients who fail their trial of void. Following inpatient surgery (such as sacrocolpopexy, uterosacral or sacrospinous ligament fixation, or colpocleisis), patients who are being discharged from the hospital with an indwelling catheter will be enrolled into the study. As per standard of care, all subjects will be scheduled for an office visit for catheter removal 24 to 72 hours after placement of the indwelling catheter per surgeon preference. Demographic information will be collected from the patients medical record (age, menopausal status, concurrent estrogen use, ethnicity, level of education, medical comorbidities, history of recurrent UTIs, and duration of hospitalization). Data regarding the patients surgical intervention (procedure type, surgical complications, operative time) will be collected from the operative record. At the time of catheter removal, subjects will be randomized to either methenamine hippurate or fluoroquinolones, using sealed, opaque, sequentially numbered envelopes. All patients, and all physicians and nurses directly involved in patient calls and clinical interaction, will be masked to treatment allocation. Only the nurses involved in catheter removal, but not decisions on the primary outcome, will open the envelope, and distribute the allocated medication to the patient, who will take one dose at the office. A 24-hour course of fluoroquinolones, as per AUA guidelines, are the first-line antibiotics for catheter removal, and will be one of the active arms of the study. Due to differences of office practice and formulary availability, the fluoroquinolone of choice at each site will be different; this is clinically relevant as different urology practices across the country use different fluoroquinolones for prophylaxis. At HUP and Radnor, the 24 hour course of fluoroquinolone used will be one dose of 500 mg of levofloxacin, as per office practice and formulary availability. At the other sites (Pennsylvania Hospital, Chestnut Hill Hospital), the 24 hour course of fluoroquinolone as per office practice will be two doses of 500 mg of ciprofloxacin, 12 hours apart. Methenamine hippurate will be given as two doses of 1g of methenamine hippurate, taken 12 hours apart. The patient will not be told which

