
medication they are taking. The methenamine, ciprofloxacin, and levofloxacin used in this study are all similar in shape, although not in color. Following catheter removal one to two hours after the first dose of medication, patients will be given a white vial or bag with the second dose of medication (if given methenamine or ciprofloxacin) and will be instructed to take second dose of the study medication at home about 12 hour later. As part of standard of care, nurses perform void trials per practice guidelines by backfilling the bladder with 300 cc normal saline, removing the catheter, and prompting the patient to void immediately. If a patient fails her trial of void, majority of the patients at our site are taught intermittent self-catheterization. If an indwelling catheter is replaced, the allocated treatment (drug or placebo) will be re-administered at repeat trial of void/repeat catheter withdrawal. No further drug will be given if the patient performs intermittent self-catheterization after the failed trial of void. FOLLOW UP VISITS: Three weekly follow-up calls and one postoperative visit are planned. It is standard of care of our clinical practices in the office for a clinical urogynecology nurses to routinely contact patients post-surgery to ask about any symptoms or complications from the procedures they underwent. In this study, per routine office practice, urogynecology nurses will call study participants once a week for the first three weeks following surgery. As per routine, using a structured form, patients will be asked about symptoms of UTI, any treatment for UTI, any urine laboratory testing, visits, and treatment for suspected UTI from other providers other than the urogynecology clinic (e.g. ER, primary care doctor), treatment of complications secondary to UTI (such as pyelonephritis and sepsis), and any additional use of antibiotic for infections other than UTI. Questions related solely to the study medication will include compliance with medications given, and side effects within 24 hours of taking medication. At any time during the study, as per standard of care of all urogynecology patients, patients who feel that they may have UTIs will be encouraged to call the urogynecology clinical nurses or the on-call physician with their symptoms. These encounters, any testing, and any empiric treatment are documented in the electronic medical system. If the diagnosis of UTI is unclear at any time, per standard of care, the patient will be asked to come into the office for physical examination and further diagnostic testing. If patients are suspected of having UTI, treatment for UTI will be initiated. As per routine office care for treatment of UTI, if possible, all patients will be asked to give a specimen for urinalysis and urine culture prior to beginning empiric treatment. Four to eight weeks following surgery, as per standard of care, patients will return to the office for a routine post-operative assessment with the investigating physicians. The patients will undergo routine post-operative physical examination and answer the above questions. Any methenamine or ciprofloxacin that has not been taken as instructed will be returned at this time. At their post-operative visit, the patient will be asked if they were aware of which medication they were taking to assess blinding.

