**Analysis Plan**

Categorical variables will be analyzed using chi-squared or Fishers exact test and parametric or non-parametric t-tests for continuous variables. Bivariable analysis will be used to determine variables (risk factors) that are independently associated with post-operative UTI. Duration of catheterization between groups will be compared using the Mann-Whitney test to compare difference in medians. The primary outcome will be the rate of clinically suspected UTI requiring treatment within the first three weeks following surgery. Comparison with fluoroquinolones will be performed using relative risk ratio. Analysis will be performed by intention to treat. If imbalances in baseline demographics are identified, multivariate analyses for post-operative UTI will be performed to control the inequality. Cost-effectiveness analysis will be performed by monetizing the collected resource utilization data in each treatment arm, including use of intervention resources, UTI treatment resources, as well as primary and secondary care resources. Incremental cost-effectiveness ratios will be calculated to compare difference in costs between prophylaxis with methenamine and prophylaxis with fluoroquinolones to the difference in effect on the incidence of post-operative UTI. Prevalence of adverse effects will be measured as

percentages. Rate of urine cultures performed by patients treated for symptomatic UTI, as well as the rate of culture-positive UTI will be noted; comparison with fluoroquinolones will be performed using relative risk ratio, with analysis by intention to treat. Positive cultures will be analyzed for percentage of uropathogen type, type of uropathogen showing resistance, and overall percentage of cultures showing resistance.

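### The primary outcome window opens at surgery but randomisation comes at catheter removal, so a UTI treated before allocation would count; the effect is probably small and cheap to remove

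*Combined protocol and SAP*

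**What the plan says.** **Start of the clock.** Primary outcome variable(s) defines the endpoint as "Treatment of clinically suspected UTI within three weeks of surgery", and spells out an event as "any symptomatic UTI requiring treatment with antibiotics as determined by the development of 2 or more of the following symptoms". The Analysis Plan repeats the window: "The primary outcome will be the rate of clinically suspected UTI requiring treatment within the first three weeks following surgery". The Abstract also counts three weeks from surgery.

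**Allocation and first dose.** Procedures states: "At the time of catheter removal, subjects will be randomized to either methenamine hippurate or fluoroquinolones". The visit is timed as follows: "all subjects will be scheduled for an office visit for catheter removal 24 to 72 hours after placement of the indwelling catheter". The first dose is taken at that visit, shortly before the catheter comes out: "Following catheter removal one to two hours after the first dose of medication". Eligibility requires that women "require post-operative short-term transurethral catheterization for greater than 24 hours", so every randomised woman has passed at least a day since catheter placement.

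**What happens in the gap.** Women are enrolled at discharge with the catheter in place. Procedures invites them to telephone with UTI symptoms at any point in the study, and treatment starts on suspicion. The weekly nurse calls run from surgery and ask about any UTI treatment.

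**What is absent.** No section restricts primary events to those after randomisation. Key exclusion criteria bars women currently using sulfonamides, but has no general exclusion for a UTI, or treatment of one, since surgery. Analysis is by intention to treat.

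**The concern.** A UTI treated before the first dose cannot be prevented by either study drug. If it counts, it adds the same expected share of events to each arm and says nothing about the comparison. Once a woman has such an event her binary outcome is fixed, whatever happens after dosing.

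In a superiority trial this kind of noise mainly costs power. In a non-inferiority trial it also pulls a real difference towards zero, which is the direction that supports the claim. Intention to treat does not correct this, because these women are properly randomised and belong in the analysis.

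The literal window also fits the stated aim poorly. Overall objectives asks about preventing UTI after short-term catheterisation, and Background places the relevant event at catheter removal. Follow-up after dosing is shortened too, to about 21 - 1 = 20 down to 21 - 3 = 18 days depending on the removal day. That shortening does not depend on arm.

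**Working it through.** **Inputs.** From Accrual: 22% event rate, 15% margin, one-sided alpha 0.025, 80% power, 120 per arm. (Study duration still gives 72 per arm; 120 is the figure that goes with the stated margin.) The share q with a pre-randomisation event is not in the documents and is assumed to be 1% to 5%.

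**The plan's own figure.** n = (1.96 + 0.8416)² × 2 × 0.22 × 0.78 / 0.15² = 7.849 × 0.3432 / 0.0225 = 119.7, so 120 per arm. This matches, and it confirms that the margin was used as an absolute risk difference.

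**Dilution.** Let the post-randomisation risks be c (fluoroquinolone) and t (methenamine). The observed risks are q + (1 - q)c and q + (1 - q)t, so the observed difference is (1 - q)(t - c).

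**Two readings of the 22%**, since Accrual does not say which applies:
- A: 22% is the post-randomisation risk and early events come on top. Then c = 0.22 and t = 0.37.
- B: 22% is the total including early events. Then c = (0.22 - q)/(1 - q) and t = c + 0.15. The observed control risk stays at 22%.

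**Test.** Non-inferiority is declared if the Wald upper 97.5% limit for the risk difference is below 15 points. The Analysis Plan names only a relative risk, so this test is assumed from the sample size. The table gives exact binomial results with 120 per arm. The false non-inferiority columns use t - c = 15 points; the power column uses equal arms.

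| q | Observed difference (points) | False non-inferiority, A | False non-inferiority, B | Power at equality, A | Observed relative risk, A |
|---|---|---|---|---|---|
| 0 | 15.00 | 2.49% | 2.49% | 80.3% | 1.68 |
| 1% | 14.85 | 2.63% | 2.64% | 79.3% | 1.65 |
| 2% | 14.70 | 2.77% | 2.80% | 78.3% | 1.62 |
| 3% | 14.55 | 2.91% | 2.98% | 77.4% | 1.60 |
| 5% | 14.25 | 3.23% | 3.35% | 75.7% | 1.55 |

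**Hand check, q = 5%, reading B.** Observed risks are 0.22 and 0.22 + 0.95 × 0.15 = 0.3625. SE = √[(0.22 × 0.78 + 0.3625 × 0.6375)/120] = 0.0579. Then (0.15 - 0.1425)/0.0579 - 1.96 = -1.83, and Φ(-1.83) is about 3.4%.

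**Where q might lie.** As an illustration only, spreading 22% evenly over 21 days gives 22/21 = 1.05% per day, or about 1% to 3% over one to three days. If events cluster after catheter removal, q is lower. If symptoms in the first days after surgery prompt empirical treatment, it is higher.

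**The case against.** **No section says early episodes will be counted.** The aim and the stated mechanism both point to UTI after removal, so the investigators may never have meant to count them. That is fair: counting follows from the literal definition together with the lack of any restriction, and an intention to count should not be inferred. The written rule still governs unless it is changed.

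**False non-inferiority depends on the estimand.** On the plan's own outcome, an observed-scale difference of 14.7 points lies inside a 15-point margin, so declaring non-inferiority would not be an error. This stands as a condition: the inflation exists only if the margin is read on post-randomisation risk. That reading fits the aim better, but it is a choice.

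**Stronger readings a reader might infer, which the documents do not support:**
- *That the comparison is biased towards non-inferiority whatever the truth.* With equal arms there is no bias.
- *That the 5-10% daily bacteriuria risk in Background bounds q.* Compounded, it gives 5% after one day at 5% and 1 - 0.9³ = 27% after three days at 10%. But the outcome requires no positive culture, so treated women need not be bacteriuric; nor is bacteriuria the same as treated symptoms. The 27% even exceeds the 22% total event rate.
- *That q could be 10%, giving about 4.5%.* With the total held at 22%, that puts 10/22 = 45% of three weeks' events before removal. Nothing in the documents suggests this.
- *That women on any antibiotic can be randomised.* Current sulfonamide users are excluded, so the gap in eligibility is partial.

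**Conclusion.** The timing mismatch is in the documents, and the direction of its effect is clear. Its size is not known, because q is not given.

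For q of 1% to 5%, false non-inferiority at a true post-randomisation excess of 15 points rises from 2.5% to about 2.6% to 3.4%. Power at equality falls from 80% to about 79% to 76% under reading A. Under reading B the observed rates at equality remain 22%, so the planned 80% is unchanged. These figures rest on the assumed q, on a Wald risk-difference test that the Analysis Plan does not name, and on reading the margin on post-randomisation risk.

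The effect is probably small, and the differing follow-up after dosing has no demonstrated consequence. The point is a cheap improvement that makes the endpoint match the aim; it is not a threat to the trial's validity.

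**What to change.** 1. Define the primary outcome as the first antibiotic treatment for a new symptomatic UTI episode starting after randomisation and within 21 days of it. Use the same wording in Primary outcome variable(s), the Analysis Plan and the Abstract.
2. Place events by treatment start date, taken from the weekly calls, the electronic record and the four-to-eight-week visit.
3. At the removal visit, record any UTI treatment since surgery, and state in the Analysis Plan how women already under treatment at that point are handled. No new exclusion is needed for this.
4. Keep the from-surgery count as a sensitivity analysis.

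The sample size can stay at 120 per arm if 22% is taken as the post-randomisation rate. The cost is slightly more date collection. Because the calls run from surgery, events in the last one to three days of the new window would come from the later visit and the record rather than from the third weekly call.
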